9.2. Adverse Events

9.2.1. Adverse Event Definitions

A TEAE is any AE either reported for the first time or worsening of a pre-existing event after the first dose of study drug until 30 to 35 days after the last dose of parsaclisib/matching placebo or ruxolitinib. Analysis of AEs (as discussed below) will be limited to TEAEs, but data listings will include all AEs regardless of their timing in relation to study drug administration.

Adverse events will be tabulated by MedDRA PT and SOC. Severity of AEs will be graded using the NCI CTCAE v5. The CTCAE reporting guidelines and grading details are available on the Cancer Therapy Evaluation Program website.

The subset of AEs considered by the investigator to be related to study drug will be considered to be treatment-related AEs. If the investigator does not specify the relationship of the AE to study drug, the AE will be considered to be treatment-related. The incidence of AEs and treatment-related AEs will be tabulated. In addition, serious TEAEs will also be tabulated.

To summarize TEAEs using the life-table method, the time to first occurrence of a TEAE is defined as the interval between the date of first dose of study drug and the date of the first

occurrence of a TEAE. Participants who have not experienced a TEAE at the time of analysis will be right-censored at the earlier of 30 to 35 days after the last dose of study drug and the date of last study visit through the end of safety follow-up. The effective sample size is defined as the number of participants at the beginning of interval minus half the participants censored in the interval. The conditional proportion is calculated as the number of first events divided by the effective sample size in the interval. If participants have missing or partial last dose dates of study drug, the partial or missing dates will be handled using the rules explained in Section 4.1.5. Any missing onset date of a TEAE will be handled according the following rules:

- If completely missing, then Day 1 will be used.
- If only the day is missing, then the first day of the month or Day 1, whichever is later, will be used.
- If both the month and day are missing, then 01 JAN of the year or Day 1, whichever is later, will be used.

9.2.2. Adverse Events of Special Interest

The following TEAEs, regardless of seriousness, will be tabulated by MedDRA PT for the safety population for each treatment group.

- Colitis
- Diarrhea of Grade 2 or higher
- Rash of Grade 2 or higher
- Pneumonitis
- Dermatitis exfoliative
- Intestinal perforation
- Cytomegalovirus infection
- Herpes simplex infection
- Herpes (varicella) zoster virus infection
- Pneumocystis jirovecii infection
- Alanine aminotransferase increased $\geq 5 \times$ ULN
- Aspartate aminotransferase increased $\geq 5 \times$ ULN

Adverse events of special interest should be captured in the eCRF.

Time to the onset of the first occurrence of each AESI will be analyzed using KM method. Median time to onset of the first occurrence of each AESI will be estimated by KM. Participants with no AESI at the time of analysis will be censored at the time of analysis.

The longest duration of AESI will be analyzed using KM method for participants in the safety population with at least one occurrence of the AESI. Median longest duration of each AESI will be estimated by KM. Participants whose AESI was not resolved at the time of analysis will be

censored at the time of the analysis. Participants with non-SAEs not resolved by 35 days after the end-of-treatment visit will be censored at 35 days after the end-of-treatment visit.

The 2 consecutive AESIs with different toxicity grades, but with the start date of the later AESI overlapped with the end date of the previous AESI, are considered 1 AESI when calculating the duration of AESI.

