9.1. General Considerations

Summary tables may be replaced with listings when appropriate. For instance, an AE frequency table may be replaced with a listing if it only contains a few unique PTs reported on relatively few participants.

Safety analyses for treatment comparisons will exclude data collected after treatment crossover. Data post-treatment crossover will be analyzed separately and descriptively without any treatment comparisons. Day 1 of crossover will be used for the crossover participants in the crossover phase.

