- Summary of TEAEs leading to parsaclisib dose reduction by MedDRA SOC and PT
- Summary of TEAEs leading to ruxolitinib dose reduction by MedDRA SOC and PT
- Summary of TEAEs leading to parsaclisib dose interruption by MedDRA SOC and PT
- Summary of TEAEs leading to ruxolitinib dose interruption by MedDRA SOC and PT
- Summary of TEAEs leading to discontinuation of parsaclisib by MedDRA SOC and PT
- Summary of TEAEs leading to discontinuation of ruxolitinib by MedDRA SOC and PT
- Summary of TEAEs by MedDRA PT: life-table method
- Summary of TEAEs by MedDRA SOC and PT: life-table method
- Summary of treatment-emergent AESIs by MedDRA PT
- Median time to the first onset of treatment-emergent AESIs by MedDRA PT
- Median longest duration of treatment-emergent AESIs by MedDRA PT

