3.2.13.2	Summary of Ruxolitinib Treatment-Related Serious Treatment-Emergent Adverse Events by MedDRA System Organ Class and Preferred Term	Safety	X
3.2.14	Summary of Treatment-Emergent Adverse Events With a Fatal Outcome by MedDRA System Organ Class and Preferred Term	Safety	X
3.2.15.1	Summary of Treatment-Emergent Adverse Events Leading to Parsaclisib Dose Reduction by MedDRA System Organ Class and Preferred Term	Safety	X
3.2.15.2	Summary of Treatment-Emergent Adverse Events Leading to Ruxolitinib Dose Reduction by MedDRA System Organ Class and Preferred Term	Safety	X
3.2.16.1	Summary of Treatment-Emergent Adverse Events Leading to Parsaclisib Dose Interruption by MedDRA System Organ Class and Preferred Term	Safety	X
3.2.16.2	Summary of Treatment-Emergent Adverse Events Leading to Ruxolitinib Dose Interruption by MedDRA System Organ Class and Preferred Term	Safety	X
3.2.17.1	Summary of Treatment-Emergent Adverse Events Leading to Discontinuation of Parsaclisib by MedDRA System Organ Class and Preferred Term	Safety	X
3.2.17.2	Summary of Treatment-Emergent Adverse Events Leading to Discontinuation of Ruxolitinib by MedDRA System Organ Class and Preferred Term	Safety	X
3.2.18	Summary of Treatment-Emergent Adverse Events by MedDRA Preferred Term: Life-Table Method	Safety	X
3.2.19	Summary of Treatment-Emergent Adverse Events by MedDRA System Organ Class and Preferred Term: Life-Table Method	Safety	X
3.2.20.1	Summary of Treatment-Emergent Adverse Events of Special Interest by MedDRA Preferred Term	Safety	X
3.2.20.2	Kaplan-Meier Estimates of Time to the First Onset of Treatment-Emergent Adverse Events of Special Interest by MedDRA Preferred Term	Safety	X
3.2.20.3	Kaplan-Meier Estimates of Longest Duration of Treatment-Emergent Adverse Events of Special Interest by MedDRA Preferred Term	Safety	X

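### AESI time-to-onset curves keep event-free participants at risk until the analysis date, although no AESI can be counted once the treatment-emergent window has closed

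*SAP*

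**What the plan says.** - **Onset rule.** SAP 9.2.2 analyses time to first occurrence of each AESI by Kaplan-Meier and reports a median. The censoring rule is: "Participants with no AESI at the time of analysis will be censored at the time of analysis".
- **What counts as an event.** The AESI list in 9.2.2 is introduced as a list of TEAEs. SAP 9.2.1 defines a TEAE as arising or worsening "after the first dose of study drug until 30 to 35 days after the last dose of parsaclisib/matching placebo or ruxolitinib", and adds: "Analysis of AEs (as discussed below) will be limited to TEAEs". The outputs carry the same label: SAP 9.2.3 lists "Median time to the first onset of treatment-emergent AESIs by MedDRA PT", and Appendix A Table 3.2.20.2 is titled "Kaplan-Meier Estimates of Time to the First Onset of Treatment-Emergent Adverse Events of Special Interest by MedDRA Preferred Term".
- **Neighbouring rules.** In the life-table analysis of time to first TEAE (SAP 9.2.1), event-free participants are "right-censored at the earlier of 30 to 35 days after the last dose of study drug and the date of last study visit", where visits count up to the close of the safety follow-up period. In 9.2.2 itself, participants whose non-serious AESI has not resolved "will be censored at 35 days after the end-of-treatment visit"; that sentence concerns duration, not onset.
- **Crossover.** SAP 9.1 states: "Safety analyses for treatment comparisons will exclude data collected after treatment crossover".
- **Data collection.** Protocol 8.3.1 monitors AEs until at least 30 to 35 days after last dose. Protocol 9.4 does not oblige investigators to look actively for SAEs after that, and Protocol 8.8.2 limits later contact to subsequent MF treatment and survival status.

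**The concern.** The event definition and the censoring rule do not share the same period of risk. Once 30 to 35 days have passed since last dose, a new AESI is outside the analysis and is no longer routinely collected. The onset rule nevertheless counts the participant as under observation and event-free until the analysis date. Nothing elsewhere in the SAP caps this for participants who stop, die or withdraw; the exclusion in 9.1 covers crossover participants only and is not part of this point.

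The inflated denominator lowers each Kaplan-Meier step. Read as on-treatment onset, the curve is too low and the median too late, and the distortion grows with the stopping rate. If the arms stop at different rates, the one with more stopping looks safer even when AESI hazards are equal. These are the events that Protocol 9.5 ties to the expected principal toxicity of the combination.

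**Working it through.** The documents give no figure for this analysis, so there is none to reproduce. The rule follows from the text; its size has to be illustrated.

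**From the documents.** The window ends up to 35 days after last dose (SAP 9.2.1), so w = 5 weeks. Enrollment lasts 1.5 years = 78 weeks (SAP 3.3). The database is frozen after the last participant's Week 24 assessments (Protocol 4.1.2), about 78 + 24 = 102 weeks after the first randomization.

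**Assumed, not in the documents.** Constant AESI hazard h; constant stopping hazard l, independent of AESI risk; no crossover; uniform entry.

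- Common AESI: 30% by Week 48, h = -ln(0.7)/48 = 0.00743 per week.
- Rarer AESI: 10% by Week 48, h = -ln(0.9)/48 = 0.00220 per week.
- Yearly stopping s of 20% or 40%: l = -ln(1 - s)/52 = 0.00429 or 0.00982 per week.

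**Curve under 9.2.2.** An onset at time t > w counts only if stopping came after t - w. All event-free participants stay at risk until cutoff, so Kaplan-Meier estimates

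F(t) = 1 - exp(-wh) + exp(-wh) × h/(h + l) × [1 - exp(-(h + l)(t - w))].

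Common AESI at Week 48:

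- s = 20%: 0.0365 + 0.9635 × 0.6339 × 0.3959 = 0.278.
- s = 40%: 0.0365 + 0.9635 × 0.4307 × 0.5238 = 0.254.
- On-treatment value: 1 - exp(-48h) = 0.300.

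| Incidence at Week 24 / 48 / 96 | On-treatment value | 9.2.2 rule, 20% stopping | 9.2.2 rule, 40% stopping |
|---|---|---|---|
| Common AESI | 16.3 / 30.0 / 51.0% | 15.8 / 27.8 / 43.7% | 15.2 / 25.4 / 36.5% |
| Rarer AESI | 5.1 / 10.0 / 19.0% | 5.0 / 9.2 / 16.0% | 4.8 / 8.4 / 13.1% |

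**Share of the risk set that can no longer have an event.** This is 1 - exp(-ht) × exp(-l(t - w)) / (1 - F(t)). For the common AESI at Week 48 with 20% stopping: 1 - 0.700 × 0.8315 / 0.7217 = 0.194. At Weeks 24 / 48 / 96 the shares are 8 / 19 / 41% at 20% stopping and 18 / 39 / 68% at 40%.

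**Median, common AESI.** The on-treatment median is ln 2 / h = 93 weeks. Under 9.2.2 it is 126 weeks at 20% stopping. At 40% the curve levels off at 0.0365 + 0.9635 × 0.4307 = 0.451, so no median is reached.

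**Checks.**

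- A 30-day window changes little: the common-AESI Week 48 values become 27.8% and 25.2%.
- Simulation of 400,000 participants with 78-week uniform entry: cutoffs at Weeks 102, 130 and 156 give the same 9.2.2 curve to within 0.002. Censoring at the end of the window gives about 30% at Week 48.
- Informative stopping (a gamma frailty with variance 1 shared by AESI and stopping, on-treatment value 0.301 at Week 48): 9.2.2 gives 0.268 at 20% stopping and 0.230 at 40%; the window rule gives 0.285 and 0.265.

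**Which weeks matter.** The documents do not date this table. At the Week 24 freeze, (102 - 48)/78 = 69% of participants could have reached Week 48 and (102 - 96)/78 = 8% Week 96. The Week 48 figures are the relevant ones there; the Week 96 figures and medians apply only to later cutoffs.

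**The case against.** The strongest defence is that the 9.2.2 curve is a valid estimate of something else. With only administrative censoring it equals the proportion of participants who actually have a treatment-emergent AESI by time t, with stopping or death as a competing event. A direct simulation at 40% stopping gave crude proportions of 15.3 / 25.4 / 36.6% at Weeks 24 / 48 / 96, matching the 9.2.2 figures above. On that reading an arm with more stopping really does have fewer treatment-emergent AESIs, and the on-treatment values are hypothetical: onset if nobody stopped. The arithmetic stands. However, the SAP names no competing event and asks for a Kaplan-Meier median time to onset, and its own time-to-first-TEAE analysis censors at the window.

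Other points stand in part:

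- Censoring at stopping can be informative, as the frailty check shows. The window rule was closer there, but not unbiased.
- The duration cap in 9.2.2 is a weak comparator because it is not an onset rule; the 9.2.1 comparison carries the weight.
- Life-table Tables 3.2.18 and 3.2.19 already give window-censored output by preferred term for AESIs listed without a grade or ULN threshold, such as colitis and pneumonitis. They do not match the Grade 2 or higher and 5 × ULN items.
- The shifts are often within sampling error. With 440/2 = 220 per arm, the binomial standard error at 27.8% is √(0.278 × 0.722/220) = 3.0 points, against a shift of 2.2. At 25.4% it is 2.9 points, against 4.6. For the rarer AESI the shifts of 0.8 and 1.6 points are below about 2 points, and its on-treatment median of 0.693/0.00220, about 316 weeks, would not be reached at realistic follow-up under either rule.
- Tables with 10 or fewer participants may become listings (SAP 9.2.3), so some rare AESIs may have no such table.

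**Conclusion.** The concern holds, as a minor point. As written, the onset rule in SAP 9.2.2 does not fit the treatment-emergent definition that governs its events, and it differs without explanation from the 9.2.1 rule for time to first TEAE.

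Under independent stopping, the downward direction for on-treatment onset does not depend on the assumed rates; the size does. For a common AESI the understatement at Week 48 is 2.2 points at 20% yearly stopping and 4.6 points at 40%; at Week 24 it is 0.5 to 1.1 points. The larger Week 96 and median effects need a common AESI, substantial stopping and a late cutoff. With identical AESI hazards, arms stopping at 20% and 40% would show 27.8% and 25.4% at Week 48.

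The display is descriptive (Protocol 10.4.2), with no test or decision rule attached. Crude AESI incidence, the life-table TEAE tables and all efficacy analyses are untouched.

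**What to change.** Replace the onset censoring sentence in SAP 9.2.2 so that participants without the AESI are censored at the earliest of:

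- the end of the TEAE window, set as one fixed day within 30 to 35 days after last dose, and naming which drug's last dose applies;
- the last study visit through safety follow-up;
- death;
- Day 1 of crossover, which makes explicit what 9.1 implies;
- the data cutoff.

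If stopping is meant as a competing event, say so and use a cumulative incidence estimator in place of the Kaplan-Meier median.

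The cost is one sentence and no new data. The drawback is that where treatment is stopped for toxicity (Protocol 6.7.6), censoring at the window may be informative, so the change reduces the bias but need not remove it. A short note to that effect beside Table 3.2.20.2 would suffice.

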8.3. Safety Assessments

8.3.1. Adverse Events

Adverse events will be monitored from the time the participant signs the ICF until at least 30 to 35 days after the last dose of study drug (parsaclisib/placebo). Adverse events that begin or worsen after informed consent should be recorded on the Adverse Events Form in the eCRF regardless of the assumption of a causal relationship with the study treatment. Conditions that were already present at the time of informed consent should be recorded on the Medical History Form in the eCRF. Adverse events (including laboratory abnormalities that constitute AEs) should be described using a diagnosis whenever possible rather than by individual underlying signs and symptoms. See Section 9 for full reporting requirements for adverse events.

Adverse events will be reported by the participant (or, when appropriate, by a caregiver, surrogate, or the participant's legally authorized representative). The investigator and any qualified designees are responsible for detecting, documenting, and recording events that meet the definition of an AE or SAE and remain responsible for following-up on AEs that are serious, considered related to the study treatment/procedures, or that caused the participant to discontinue the study treatment. Care will be taken not to introduce bias when detecting AEs and/or SAEs. Open-ended and nonleading verbal questioning of the participant, such as "How are you feeling?," is the preferred method to inquire about AE occurrences. Adverse events may also be detected when they are volunteered by the participant during the screening process or between visits or through physical examinations, laboratory tests, or other assessments. The definition, reporting, and recording requirements for AEs are described in Section 9.

All SAEs will be reported to the sponsor or designee within 24 hours. The investigator will submit any updated SAE data to the sponsor within 24 hours of it being available.

After the initial AE/SAE report, the investigator is required to proactively follow each participant at subsequent visits/contacts. All SAEs, and nonserious AEs of special interest (as defined in Section 9.5), will be followed until resolution, stabilization, the event is otherwise explained, or the participant is lost to follow-up (as defined in Section 7.3).

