9.3. Recording and Follow-Up of Adverse Events and/or Serious Adverse Events

Adverse Event and Serious Adverse Event Recording
 
• An AE/SAE that begins or worsens after informed consent is signed should be recorded on the Adverse Event Form in the eCRF. Conditions that were present at the time informed consent was given should be recorded on the Medical History Form in the eCRF.• When an AE/SAE occurs, it is the responsibility of the investigator to review all documentation (eg, hospital progress notes, laboratory reports, and diagnostic reports) related to the event.• The investigator (or delegate) will then record all relevant AE/SAE information in the eCRF.• It is not acceptable for the investigator to send photocopies of the participant's medical records in lieu of completing the Adverse Event Form in the eCRF.• There may be rare instances when copies of medical records for certain cases are requested. In this case, all participant identifiers, with the exception of the participant number, will be redacted by the site staff on the copies of the medical records before submission. These records can be submitted to Incyte Pharmacovigilance by email/fax per the contact information listed in the Study Binder.• The investigator will attempt to establish a diagnosis of the event based on signs, symptoms, and/or other clinical information. Whenever possible, the diagnosis (not the individual signs/symptoms) will be documented as the AE/SAE. When a clear diagnosis cannot be identified, each sign or symptom should be reported as a separate AE/SAE. 
To the extent possible, each AE/SAE should be evaluated to determine the following:
 
• The severity grade (CTCAE v5.0 Grade 1 to 5). See below for further instructions on the assessment of intensity.• Whether there is at least a reasonable possibility that the AE is related to the study treatment: suspected (yes) or not suspected (no). See below for further instructions on the assessment of causality.• The start and end dates, unless unresolved at the final safety follow-up visit.• The action taken with regard to parsaclisib/matching placebo and ruxolitinib as a result of the AE/SAE(s).• The event outcome (eg, not recovered/not resolved, recovered/resolved, recovering/resolving, recovered/resolved with sequelae, fatal, unknown).• The seriousness, as per the SAE definition provided in Section 9.2.• The action taken with regard to the event. Note: If an AE is treated with a concomitant medication or nondrug therapy, this action should be recorded on the Adverse Event Form and the treatment should be specified on the appropriate eCRF (eg, Prior/Concomitant Medications, Procedures and Non-Drug Therapy).

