9.4. Reporting of Serious Adverse Events

Regardless of suspected causality (eg, relationship to study drug, reference therapy, or study procedure[s]), all SAEs occurring after the participant has signed the ICF through 30 to 35 days after the last dose of study treatment or until the participant starts a new MF therapy, whichever occurs earlier, must be reported to the sponsor (or designee) within **24 hours** of learning of its occurrence, unless otherwise specified by the Protocol. The investigator will submit any updated SAE data to the sponsor (or designee) within 24 hours of it being available. For Japan, this information must also be reported immediately to the head of the study site.

Investigators are not obligated to actively seek SAE information after the safety follow-up visit or 30-35 days after the last dose of study treatment. If the investigator learns of any SAE, including death, at any time after this period, and he/she considers the event to be reasonably related to the study treatment or study participation, then the investigator must notify the sponsor (or designee) within 24 hours of becoming aware of the event.

After the initial AE/SAE report, the investigator is required to proactively follow each participant at subsequent visits/contacts. All SAEs and AESIs (as defined in Section 9.5) will be followed until resolution, stabilization, the event is otherwise explained, or the participant is lost to follow-up (as defined in Section 7.3).

Prompt notification by the investigator to the sponsor regarding an SAE is essential so that legal obligations and ethical responsibilities toward the safety of participants and the safety of a study treatment under clinical investigation are met.

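### Unresolved serious AESIs are censored at the analysis date with no bound at death, withdrawal or last contact, so the median longest duration can be overstated

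*SAP*

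**What the plan says.** SAP 9.2.2 states that "The longest duration of AESI will be analyzed using KM method for participants in the" safety population with at least one occurrence of the event. Two censoring rules follow.

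- General rule: "Participants whose AESI was not resolved at the time of analysis will be" "censored at the time of the analysis".
- Exception: "Participants with non-SAEs not resolved by 35 days after the end-of-treatment visit will be censored at 35 days after the end-of-treatment visit".

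Neither rule mentions death, withdrawal or loss to follow-up. The result is a planned output (SAP 9.2.3; SAP Appendix A, Table 3.2.20.3).

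Two protocol sections bear on how the rule works. Protocol 9.3 lists event outcomes that include "recovered/resolved with sequelae, fatal, unknown", so fatal and unknown are separate from resolved. Protocol 9.4 says that SAEs and AESIs "will be followed until resolution, stabilization, the event is otherwise explained, or the participant is lost to follow-up", so observation of an event can end while the event is still open.

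**The concern.** A Kaplan-Meier risk set should contain only people who are still under observation for the event, which here is resolution of the AESI. Under the general rule, a participant with a serious AESI who dies or is lost on day 10 counts as observed and unresolved until the analysis date. SAP 3.3 expects the survival analysis about 3 years after the first randomization, so that unobserved stretch can be long.

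The SAP bounds its other time-to-event measures by actual observation:

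- SAP 9.2.1 stops the TEAE life table at the last study visit, or 30 to 35 days after the last dose if that is earlier.
- SAP 7.4.3 stops overall survival at the last known alive date or the data cutoff, whichever is earlier.
- SAP 7.4.1.2 stops spleen-response duration at the last assessment.

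What is at stake is the reported duration of serious immune-related and infectious toxicity, which Protocol 9.5 treats as the principal expected risk of the combination.

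**Working it through.** The plan states no AESI count, duration or fatality figure, so there is nothing to reproduce. The check covers direction first, then size under stated assumptions.

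**Direction.** The estimate is S(t) = Π(1 − d/n) over resolution times, where d is the number resolving and n the number at risk. Moving a censoring date later leaves every d unchanged and leaves every n unchanged or larger. Each factor therefore stays the same or rises, and so does the median.

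**Small example (invented data).** Ten participants: seven resolve on days 5, 8, 10, 14, 21, 28 and 35; three die or are lost on days 6, 9 and 12. The median is the first time S is 0.5 or less.

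- SAP rule, all three kept at risk: S = 0.9, 0.8, 0.7, 0.6, 0.5 at days 5, 8, 10, 14, 21. Median 21 days.
- Censored at death or last contact: 9/10 = 0.900 (day 5); × 7/8 = 0.788 (day 8); × 5/6 = 0.656 (day 10); × 3/4 = 0.492 (day 14). Median 14 days.
- Death or loss counted as the end of the event: ends on days 5, 6, 8, 9, 10 bring S to 0.5. Median 10 days.

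**Size in large samples.** Assumptions: exponential resolution with a true median of 21 days, so λ = ln 2 / 21 = 0.0330 per day; an independent exponential hazard of death or loss, μ = λf/(1 − f), where f is the share of cases in the analysis that end in death or loss before resolution; all affected cases are serious, and the analysis date falls after the times that matter. Under the SAP rule the proportion resolved by t is (1 − f)(1 − exp(−λt/(1 − f))). Setting this to 0.5 gives

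t = −(1 − f) · ln(1 − 0.5/(1 − f)) / λ.

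For f = 20%: 1 − 0.5/0.8 = 0.375, and −0.8 × ln(0.375) / 0.0330 = 23.8 days. Censoring at death or last contact gives 21.0 days for every f.

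| f | SAP rule (days) | Bounded rule (days) | Overstatement |
|---|---|---|---|
| 5% | 21.5 | 21.0 | 2% |
| 10% | 22.1 | 21.0 | 5% |
| 20% | 23.8 | 21.0 | 13% |
| 30% | 26.6 | 21.0 | 27% |
| 40% | 32.6 | 21.0 | 55% |
| 50% or more | not reached | 21.0 | – |

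**Size in a finite sample.** A simulation used 40 cases per term, analysis dates 100 to 700 days after onset and 2000 replicates. The typical median under the SAP rule against the bounded rule was 20.7 vs 20.6 days at f = 5%, 22.9 vs 21.0 at 20% (9% higher) and 30.3 vs 21.2 at 40%. The SAP-rule median was not reached in 8% of replicates at f = 40% and in 45% at f = 50%. The direction agrees with the table; the shifts are somewhat smaller.

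**The case against.** Several points on the other side carry weight.

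- **Death is not mentioned.** SAP 9.2.2 is silent on death, and Protocol 9.3 asks for event end dates. Programming might close a fatal AESI on the date of death. That is possible, but nothing says so, and with fatal listed apart from resolved the literal rule keeps the event open. A serious AESI in a participant lost to follow-up is the firmer case.
- **Keeping deaths at risk has an interpretation.** If only deaths are involved, the curve approximates the cumulative incidence of resolution among all cases. But the SAP calls the result a median duration, and this reading does not rescue losses to follow-up, whose events may have resolved unseen.
- **Sparse terms may never reach a table.** SAP 9.2.3 allows a listing when 10 or fewer participants appear.
- **Fatal toxicity is not hidden.** Fatal and serious TEAEs and AESI incidence are tabulated separately.

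A reader might also infer more than the documents support:

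- *That every unresolved AESI runs to the analysis date.* Nonserious events are capped.
- *That a participant who dies early adds years of duration to the estimate.* A censored time only keeps the participant in the risk set; once it passes the last observed resolution, a later date changes nothing.
- *That the arm with more serious AESIs is distorted more.* The effect follows the share of cases ending in death or loss; twice as many cases at the same share gives the same expected shift.
- *That the 35-day cap contradicts the protocol and must go.* Protocol 8.3.1 and 9.4 set data-collection duties, and follow-up there can also stop at stabilization or loss. A fixed analysis cut-off at the end of the safety follow-up window gives up some information but is defensible, and it does not cause the overstatement.

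**Conclusion.** The point holds for serious AESIs. As written, SAP 9.2.2 lacks the observation-based bound used elsewhere in the SAP, and following it can only leave the median longest duration unchanged or raise it. The size is unknown because the documents give no rate of death or loss among AESI cases. Under the assumed 21-day true median and independent exponential hazards, the large-sample overstatement runs from about 2% at a 5% share to 13% at 20% and 55% at 40%, with no median at 50% or more. A small share makes it negligible; a term with few cases and a high share is where it would show. Any between-arm distortion requires that share to differ between arms. The crossover truncation in SAP 9.1 limits the extra time only for participants who cross over.

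The adjacent rule for time to first onset has the same gap: participants with no AESI are censored at the time of analysis, whenever their observation ended.

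These are descriptive safety summaries without a test, so the primary and key secondary conclusions do not depend on them. This is a minor correction.

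**What to change.** In SAP 9.2.2:

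1. Censor unresolved AESIs at the earliest of the last AE assessment or contact, death and data cutoff. Keep the 35-day cap for nonserious events as an additional limit.
2. State how death before resolution is treated: censored, or analyzed as a competing risk. The choice matters, and the small example shows why counting death as the end of the event is unattractive: it gives the shortest median (10 days, against 14 with censoring) and makes rapidly fatal toxicity look brief.
3. Report the number of fatal AESIs beside each median, so that the duration is not read without them.
4. Apply the same observation bound to time to first onset, in line with SAP 9.2.1.

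The cost is a few sentences in the SAP and a change to the censoring-date derivation. No new data are needed, and sample size, alpha and the primary and key secondary analyses are untouched.
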